5.3 Participant Recruitment

We estimate that we will need to enroll 206 participants with MCI and sleep apnea in order to have 80% power to detect a minimal clinically significant change in the SDMT of 3.8 points assuming CPAP adherence of 62% and loss-to-follow-up of 10%. In our data, the prevalence of moderate or greater OSA among patients with MCI is ~50% (Figure 1). Assuming that of these ~25% will already be on CPAP, this would require identifying ~550 adults with MCI who would be willing to participate in the study. In order to reach ~550 of these individuals, we will use a combination of the following recruitment strategies:

- 1) **Geotargeted mailings.** We will send geotargeted mailings to adults in the GTA over the age of 55, inviting those with cognitive concerns and symptoms compatible with sleep apnea to go to our study website. A similar approach was used in the Canadian Consortium on Neurodegeneration in Aging Can Thumbs Up Brain Health Support Program (CTU-BHSP) study. In CTU-BHSP, one participant enrolled for every 130 postcards mailed, of which 1/3 had MCI. We plan to send out up to 40,000 postcards, which should yield ~100 interested potential participants with MCI. We will retain the option to scale up as needed to increase enrolment.
- 2) **Online advertisements.** We will produce geotargeted ads to run through Instagram and Facebook. A similar approach was used in the CTU-BHSP study, where \$500 spent on geotargeted Facebook and Instagram advertising to reach 39,000 adults resulted in 18 enrolled participants with MCI. We plan to run an advertising campaign with double the reach of CTU-BHSP, which should yield ~40 interested potential participants with MCI. We will retain the option to scale up as needed to increase enrolment.
- 3) **Clinic-based recruitment.** We will recruit from Toronto Dementia Research Alliance affiliated clinics at the Toronto Western Hospital, Baycrest Hospital, and Sunnybrook hospital. Collectively, these clinics see ~80 patients with MCI per month. Between these three clinics, we anticipate recruiting up to 10 adults with MCI per month over 24 months. This should yield ~240 interested potential participants with MCI. Flyers will be placed in clinic rooms and/or bulletin boards and will also be available for potential participants to take home. Potential participants may also be approached by a member of their care team who can provide them with a study flyer which will contain contact information for the study. Potential participants will be given the opportunity to verbally agree with their clinic care team to share contact information (name, phone, email) with study staff so that they may be contacted to discuss interest in participating in this study. If applicable, potential participants may also consent for clinical information relevant to this protocol (i.e. MCI diagnosis, cognitive test results) to be shared with the study team.
- 4) **Baycrest Centre.** The Baycrest Centre offers a number of recruitment sources, including but not limited to:

- a. **Rotman Database:** The Rotman Research Institute manages a database of research volunteers, with >16,000 active participants. Some of these individuals have received a diagnosis of MCI.
- b. **Cogniciti.** The Cogniciti Brain Health Registry (www.cogniciti.com), based at Baycrest, includes >10,000 individuals in the GTA who have undergone online cognitive testing and who have also indicated their desire to be contacted about clinical trials. We anticipate based on pilot work that we will find 1,200 adults with MCI. An already established pipeline is in place in [name] lab (co-PI of this protocol) to screen these individuals by videoconferencing for MCI. This should yield ~300 interested potential participants with MCI, with option to scale up as needed to increase enrolment. Potential participants may also be provided a study flyer which will contain contact information for the study. Potential participants will be given the opportunity to verbally agree to share contact information (name, phone, email) with study staff so that they may be contacted to discuss interest in participating in this study. If applicable, potential participants may also consent for clinical information relevant to this protocol (i.e. MCI diagnosis, cognitive test results) to be shared with the study team.
- c. **Kimel Family Centre for Brain Health.** The Kimel Centre (<https://kimelcentre.baycrest.org/>) is enrolling 2,000 individuals aged 50 or over interested in dementia prevention, all of whom are screened cognitively prior to entry in programs. These individuals are entered into the Rotman database at Baycrest and given the opportunity to indicate their desire to be contacted about clinical trials. We anticipate of these 2,000 participants, 600 will have MCI based on their cognitive evaluations. Through [name] (co-PI of this protocol and Scientific Director of the Kimel Centre, and also [name], Associate Scientific Director of the Kimel Centre), this should yield ~400 interested potential participants with MCI, with an option to scale up as needed to increase enrolment. Kimel Centre participants will be reached through 5 mechanisms: 1) through the Rotman database 2) through physical flyers placed in Kimel Centre spaces 3) through regular email newsletters sent out by the Kimel Centre 4) in person by Kimel centre staff during Kimel clinic visits, and 5) the study PI will conduct a series of in-person education sessions at the Kimel centre addressing sleep more broadly and also this study more specifically.. For 1) Kimel Centre staff will identify Kimel Centre participants who are already part of the Rotman database who have already consented to recontact and will provide their contact information (name, phone, email) to our study staff. For 2) the physical flyers will direct participants to the study website / study email address / study phone. For 3) the newsletters will direct potential participants to the study website / study email address / study phone. For 4) Kimel Centre staff will a) provide participants with a study flyer and b) obtain consent from potential participants to share contact information with our study staff. For 5) at the conclusion of in-person education sessions hosted by the study PI, attendees will be provided the physical flyer for the study, directing them to the study website / study email address / study phone. If applicable, potential participants may also consent for

clinical information relevant to this protocol (i.e. MCI diagnosis, cognitive test results) to be shared with the study team. Finally,

- d. **Baycrest cognitive neurology clinics:** Flyers will be placed in clinic rooms and/or bulletin boards and will also be available for potential participants to take home. Potential participants may also be approached by a member of their care team who can provide them with a study flyer which will contain contact information for the study. Potential participants will be given the opportunity to verbally agree with their clinic care team to share contact information (name, phone, email) with study staff so that they may be contacted to discuss interest in participating in this study. If applicable, potential participants may also consent for clinical information relevant to this protocol (i.e. MCI diagnosis, cognitive test results) to be shared with the study team.

5.4 Participant Screening

Potential participants, irrespective of the recruitment source, will be required to proceed to the study website where they will fill out a short REDCap-hosted online questionnaire. The questionnaire will include collection of basic demographics and subjective sleep and cognitive information, limited to information necessary for determining eligibility. This includes email address, phone number, and implied consent to be contacted by study staff for additional screening.

Potential participants who fill out the REDCap-hosted online questionnaire will be contacted by study staff to assess eligibility. This includes:

- 1) An in-depth video-conference to establish a diagnosis of MCI and to confirm all inclusion/exclusion criteria. This will consist of a clinical interview, Logical Memory II, MoCA, and Lawton-Brody Instrumental Activities of Daily Living Scale Score, as well as screening for clinically significant insomnia (Insomnia severity index>15) or restless legs syndrome (Cambridge Hopkins questionnaire). 2) If MCI confirmed, participants will be mailed a home-based sleep apnea test (HSAT), namely the Apnealink which will be self-administered. With our community-based recruitment model, using a HSAT is necessary to minimize the number of participants without sleep apnea who need to undergo polysomnography. The Apnealink is considered a Type 4 sleep monitor by the American Academy of Sleep Medicine and has been validated against polysomnography. 3) Individuals who screen positive for OSA on the HSAT will meet with a study physician by video call or in person prior to in-lab PSG. The study physician will confirm inclusion and exclusion criteria, including positive results for both MCI and OSA, and will perform a standard clinical assessment to ensure clinical appropriateness of and eligibility for CPAP. The participant will then be scheduled for an in-lab PSG. 4) Participants that meet the criteria for MCI and OSA, and satisfy all other inclusion/exclusion criteria, will have a video-conference with study staff to discuss the final determination of eligibility, obtain informed consent, and to unlock their randomization assignment.

5.5 Screen Failures

Participants that do not meet the criteria for MCI or OSA, or do not meet all of the inclusion criteria or have at least one of the exclusion criteria at any stage of the screening process are deemed as screen failures and will have a video-conference with study staff to discuss their

reason for not being eligible. These participants who have failed the screening criteria are ineligible for participation and will be informed that they do not meet the study's inclusion criteria and they will be thanked for their time. They will be encouraged to try to participate in future studies for which they may be eligible, and they will have an opportunity to ask questions pertaining to their screening for this study. Screen information will be retained as part of the trial for further analyses.

5.6 Randomization and Blinding

Participants will be randomized 1:1 to one of the following groups:

Early CPAP group: Brain Health Support PRO sleep modules (BHP-sleep; a web-based sleep education platform) and Continuous Positive Airway Pressure (CPAP) for 8 months; or

Later CPAP group: BHP-sleep for first 4 months, then BHP-sleep and CPAP for remaining 4 months of participation.

From the beginning of month 5 until the end of month 8, both groups will be receiving CPAP.

Randomization will be performed using an instance of the OxMAR software package hosted on a Sunnybrook Research Institute computer. Randomization will be carried out in blocks of 2 and stratified such that equal numbers from each recruitment type (i.e. clinic, community) will be in each group.

Research personnel not involved in assessments or interventions will access the randomization list to allocate participants in each group. Personnel performing outcome assessments and methodologists performing analyses will be blinded to group allocation. Randomization will be completed by a dedicated analyst, who will distribute randomization codes (using a random number generator) to determine the treatment arm to which each participant is allocated. Assessors and Research Assistants administering the interventions will be blinded and as such, only the analyst overseeing randomization will have access to the password-protected randomization list.

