12.4 Consent

Informed consent is a process that is initiated prior to the individual agreeing to participate in the study and continues throughout study participation. A consent form describing in detail the study procedures and risks will be reviewed with and given to each participant. Consent forms will be REB-approved, and the participant is required to read and review the document or have the document read to him or her. The investigator or designee will explain the research study to the participant and answer any questions that may arise. The participant will sign the informed consent document prior to any study-related assessments or procedures. Participants will be given the opportunity to discuss the study with their surrogates or think about it prior to agreeing to participate. They may withdraw consent at any time throughout the course of the study. A copy of the signed informed consent document will be given to participants for their records.

Prior to involvement in any study-related activities, consent must be obtained in writing for each participant using the current REB approved informed consent form. It is the responsibility of the investigator to ensure that all advertisements and written information, including the informed consent form, disseminated to participants has been approved by the local REB prior to use. The ethics approved Informed Consent Form (ICF) and any other written information, must be provided to each participant, allowing ample time to ask and have answered any questions prior to making a decision regarding participation. Neither the investigator nor study staff should unduly influence or coerce a participant to participate in the study.

The ICF will be signed and dated by the participant and individual obtaining consent. The consent process will be documented in the clinical or research record.

The original ICF, in its entirety, will be maintained by the site, and a complete copy of the signed ICF provided to the participant. The rights and welfare of the participants will be protected by emphasizing to them that the quality of their clinical care will not be adversely affected if they decline to participate in this study.

The provision of consent is an ongoing process and should be maintained throughout the duration of the study. Participants may withdraw consent at any time throughout the course of the study.

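### Section 5.6 publishes a single block size of 2 in an unmasked CPAP comparison, so up to half of the assignments can be foreseen without access to the list; secondarily, the arm is unlocked before the baseline SDMT.

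*Protocol*

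**What the plan says.** Section 5.6 fixes the scheme: "Randomization will be carried out in blocks of 2 and stratified such that equal numbers from each recruitment type" (clinic or community) enter each group. The ratio is 1:1, and no other or varying block size is mentioned. Its safeguards are separate allocators ("Research personnel not involved in assessments or interventions will access the randomization list to allocate participants in each group"), blinded outcome assessors, and a restricted list ("only the analyst overseeing randomization will have access to the password-protected randomization list").

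Section 4.1 describes a single-blinded trial of 206 adults. One arm starts CPAP at once and the other has web education alone for four months. No sham is described.

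Section 5.4 ends screening with a video call to "discuss the final determination of eligibility, obtain informed consent, and to unlock their randomization assignment". Appendix B puts randomization in a pre-baseline row and the first SDMT in the later Week 0 row. No SDMT is listed at screening. Section 9.4 adjusts the primary 4-month comparison for baseline SDMT.

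**The concern.** In a 1:1 block of 2, the second assignment is fixed by the first. The block size is printed in the protocol, recruitment type is visible to staff, and the arm becomes visible once a participant does or does not receive CPAP. Someone following a stratum can therefore work out the next assignment without opening the list, which is the only route that the password closes. Foresight could influence when an assignment is unlocked or how strongly a candidate is encouraged.

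The second issue is the order of events. Baseline SDMT is normally valued as a covariate because allocation cannot have affected it. Here it is taken after the unlock, probably by a participant who knows the arm. Participants also know their arm at Week 16, so concealed allocation and a pre-allocation baseline are two protections still open to this design.

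**Working it through.** **Inputs.** Block size 2, ratio 1:1 and two strata (5.6); 206 randomized (9.2); test-retest correlation 0.78 (9.2); three-year study (Protocol Summary) with eight months of participation. The protocol gives no figure for predictability, so there is none to reproduce.

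**Blocks of 2.** The two sequences are AB and BA.
- Certain: one assignment in two, 1/2 × 206 = 103. If both strata hold an odd 103, it is 2 × 51 = 102.
- Guessed correctly: (0.5 + 1)/2 = 0.75.
- If each earlier arm is known with probability p: certain = 0.5p, guessed = 0.5 + 0.25p. At p = 0.5 this gives 0.25 (about 51 of 206) and 0.625. At p = 0.25 it gives 0.125 and 0.5625.

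**Alternatives.** Fixed blocks of 4 and 6 were enumerated exactly. The random mix (4 or 6, probability 1/2 each) was simulated against a predictor who knows both sizes and updates on everything seen.

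| Scheme | Earlier arms known | Certain | Guessed |
|---|---|---|---|
| Blocks of 2 | all | 50% | 75% |
| Fixed 4 | all | 33% | 71% |
| Fixed 6 | all | 25% | 68% |
| Mix of 4 and 6 | all | about 5.5% | 69% |
| Blocks of 2 | half (assumed) | 25% | 62% |
| Mix of 4 and 6 | half (assumed) | 0.2% | 59% |
| Blocks of 2 | quarter (assumed) | 12% | 56% |
| Mix of 4 and 6 | quarter (assumed) | 0.01% | 55% |

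If all arms are known but not the stratum, blocks of 2 give about 12% certain and 69–71% guessed.

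**Pace.** Section 5.3 gives 24 months for clinic recruitment; 36 − 8 = 28 months is the longest window that fits the study. With even accrual (assumed), 206/24 = 8.6 and 206/28 = 7.4 randomizations a month over both strata, a sequence that one person could follow.

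**Price of the mix.** The largest final imbalance was 3 in a stratum, so the worst case overall is 106 versus 100. Relative efficiency is 4 × 106 × 100/206² = 0.9992.

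**Timing of the unlock.** The adjusted difference is (difference at Week 16) − b × (difference at baseline). Take b = 0.78, which assumes equal SDs and that an unadjusted 19-month correlation applies. Let awareness of the arm shift one group's score by d:

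| Where the shift occurs | Bias, present order | Bias, battery before unlock |
|---|---|---|
| Baseline only | −0.78d | 0 |
| Baseline and Week 16 equally | d − 0.78d = 0.22d | 1.0d |
| Week 16 only | 1.0d | 1.0d |

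The documents do not say which row applies or how large d is.

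**The case against.** The strongest reply is that foresight has little to act on. PSG thresholds are numeric, and "The study physician will confirm inclusion and exclusion criteria". Allocators are separate from assessors and intervention staff. People unwilling to start CPAP are excluded, and both arms receive it from month 5, so the motive to steer anyone is weaker than with a never-treated control. The ceiling also needs the block size, the stratum order and every earlier arm. With partial knowledge, the mix improves guessing by only one to three percentage points. All of this stands and limits the weight of the point. It does not answer the loss of concealment itself: the gain lies in removing certain assignments, and it costs almost nothing.

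On the unlock, the reply is stronger. The reorder is not uniformly protective: if awareness moves both scores equally, it raises the residual bias from 0.22d to 1.0d. The protocol also does not state outright that the arm is announced to the participant on the call.

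Three stronger readings are tempting and not supported:
- That allocation is in fact compromised. The documents show only that it could be foreseen.
- That foresight can decide who consents, because 5.4 mentions consent at the unlock call. Section 12.4 says "The participant will sign the informed consent document prior to any study-related assessments or procedures", and Appendix B lists consent at the first screening video call.
- That assessor blinding fails, because Appendix B gives one coordinator/RA label to the randomization call, the SDMT and mask fitting. A staff category does not show that one person does all three; 5.6 requires blinded assessors, and 6.1.3 gives mask fitting to a sleep technologist.

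**Conclusion.** The block-size point holds and should be fixed. A fixed, published block of 2 lets up to 50% of assignments be known in advance and 75% be guessed. These are ceilings that assume the stratum and its earlier arms are known; the lower figures rest on assumed partial knowledge. No bias is demonstrated, and its size cannot be derived from the documents.

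The timing of the unlock is a secondary, good-practice point. The sequence is clear from 5.4 and Appendix B; awareness of the arm at the baseline test is probable rather than stated. A reader might infer that each point of baseline shift biases the result by 0.78 point and that reordering cures it. That is one of three cases, and the documents favour none.

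**What to change.** 1. In 5.6, replace the fixed block size with randomly varying block sizes (for example 4 and 6) within the same two strata, and hold the sizes in a restricted randomization document. The cost is a new list and a wording change, with imbalance of at most 3 per stratum, 99.9% relative efficiency at worst, and N still 206.
2. Where the visit can be staffed, keep the pre-baseline call for eligibility and unlock the assignment only after the Week 0 cognitive battery, amending 5.4 and Appendix B. If mask fitting stays at the baseline visit as 6.1 states, a technologist must be available at all 206 Week 0 visits instead of about 103 known in advance. Section 6.1.3 mentions one full-time technologist; whether that suffices cannot be judged from the protocol.

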5.7 Participant Withdrawal and Discontinuation of Study Procedures

At their own discretion, participants may withdraw from the study at any time and for any reason. Study participants may also be withdrawn from the study at the discretion of an investigator for reasons such as, but not limited to safety, participant compliance or behavioral concerns.

Participants withdrawing from the study should be contacted by the study research team requesting a final visit and to follow up with any unresolved adverse events. Once withdrawn from the study, no further study procedures or evaluations should be performed, or additional study data collected. However, every effort should be made to obtain permission to document the reason for withdrawal and to collect participant outcomes, such as survival data up to the protocol-described end of participant follow up period, where possible. Any data collected prior to the withdrawal of consent may be retained and used by the sponsor.

6 INTERVENTIONS

6.1 Continuous positive airway pressure (CPAP)

Participants randomized to the Early CPAP group will receive a study-provided auto-tiltrating CPAP device, with settings set by one of the study sleep medicine physicians according to current clinical practice parameters (9). Participants will undergo an in-person mask fitting at their baseline study visit, and then will be supported by a sleep technologist with extensive clinical experience with CPAP who will contact participants by telephone or video call. Masks, tubing, chin straps, and other equipment necessary to optimize CPAP adherence will be provided by the study as necessary to optimize adherence, which will be tracked through participants' CPAP devices.

At the start of the 5th month, participants in the Later CPAP group will receive a study-provided auto-tiltrating CPAP device following the same protocol.

